6.3 Study Duration

Patient enrollment is expected to occur over a 52-month period, with follow-up continuing for a minimum of 12 months on each patient. Total study duration is expected to be approximately 60 months. Please consult [Section 7.6.2](#) regarding recommended procedures and follow-up after treatment discontinuation.

6.4 Study Completion

The study is considered complete when sufficient information is available to enable assessment of the primary endpoint and selected secondary endpoints. The **Study Completion** date will be the date beyond which study data are no longer entered into the primary database (this study completion date generally precedes the date on which the database lock occurs by several weeks/months).

7 Study Treatment Identification, Administration, and Schedule

7.1 Product Manufacturing and Characterization

Refer to the [Investigator Brochure \(IB\)](#) for full details of product manufacturing and characterization.

7.2 Recommended Medications Per Institutional Guidelines/Practices

It is recommended that patients receive the following types of prophylactic therapies/regimens per institutional guidelines/practices:

- Antibacterial: ciprofloxacin, levofloxacin, or an equivalent antibiotic
- Antifungal: fluconazole, voriconazole, or an equivalent antifungal
- Antiviral: acyclovir, valacyclovir or an equivalent antiviral

7.3 Allowed Medications/Therapies

All patients may receive supportive care measures as clinically indicated, including prophylactic antibiotics, antihistamines, antiemetics, albumin, fluids (hydration), and supportive measures. Patients may receive growth factor support and/or blood product transfusions as per the discretion of their physician.

Albumin 25 g IV daily should be administered if serum albumin is between 3.0-3.5 g/dL (30-35 g/L) on days that dosing occurs or if it is <3.0 g/dL (30 g/L) on days when treatment has been withheld or in the immediate post-treatment period. The Investigator has discretion with regard to frequency of administration per product and institutional guidelines.

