16.5 Appendix E. CLS Management Guidance

Time of Presentation	CLS Sign/Symptom	Recommended Action	ELZONRIS Dosing Management
Prior to first dose of ELZONRIS in cycle 1	Serum albumin < 3.2 g/dL	Administer ELZONRIS when serum albumin \geq 3.2 g/dL.	
During ELZONRIS dosing	Serum albumin < 3.5 g/dL		Interrupt ELZONRIS dosing until the relevant CLS sign/symptom has resolved ¹ .
	Serum albumin reduced by \geq 0.5 g/dL from the albumin value measured prior to ELZONRIS dosing initiation of the current cycle	Administer 25g intravenous albumin (q12h or more frequently as practical) until serum albumin is \geq 3.5 g/dL AND not more than 0.5 g/dL lower than the value measured prior to dosing initiation of the current cycle.	
	A predose body weight that is increased by \geq 1.5 kg over the previous day's predose weight	Administer 25g intravenous albumin (q12h or more frequently as practical), and manage fluid status as indicated clinically (e.g., generally with intravenous fluids and vasopressors if hypotensive and with diuretics if normotensive or hypertensive), until body weight increase has resolved (i.e. the increase is no longer \geq 1.5 kg greater than the previous day's predose weight).	
	Edema, fluid overload and/or hypotension	Administer 25g intravenous albumin (q12h, or more frequently as practical) until serum albumin is \geq 3.5 g/dL. Administer 1 mg/kg of methylprednisolone (or an equivalent) per day, until resolution of CLS sign/symptom or as indicated clinically. Aggressive management of fluid status and hypotension if present, which could include intravenous fluids and/or diuretics or other blood pressure management, until resolution of CLS sign/symptom or as clinically indicated.	

¹ ELZONRIS administration may resume in the same cycle if all CLS signs/symptoms have resolved and the patient did not require measures to treat hemodynamic instability. ELZONRIS administration should be held for the remainder of the cycle if CLS signs/symptoms have not resolved or the patient required measures to treat hemodynamic instability (e.g. required administration of intravenous fluids and/or vasopressors to treat hypotension) (even if resolved), and ELZONRIS administration may only resume in the next cycle if all CLS signs/symptoms have resolved, and the patient is hemodynamically stable.

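### Section 7.3, the Synopsis and Appendix E call for albumin replacement at different albumin levels, and nothing says which governs

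*Protocol*

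**What the plan says.** Section 7.3 opens with a general permission: "All patients may receive supportive care measures as clinically indicated, including prophylactic antibiotics, antihistamines, antiemetics, albumin, fluids (hydration), and supportive measures". It then gives a specific rule: "Albumin 25 g IV daily should be administered if serum albumin is between 3.0-3.5 g/dL (30-35 g/L) on days that dosing occurs". The same sentence sets a second threshold, below 3.0 g/dL, for other days: "30 g/L) on days when treatment has been withheld or in the immediate post-treatment period". It closes with "The Investigator has discretion with regard to frequency of administration per product and institutional guidelines". The Allowed Medications/Therapies paragraph of the Synopsis repeats the rule with similar discretion on frequency.

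Appendix E lists two albumin signs during dosing. One is "Serum albumin < 3.5 g/dL". The other is a reduction of at least "0.5 g/dL from the albumin value measured prior to ELZONRIS dosing initiation of the current cycle". The recommended action is "Administer 25g intravenous albumin (q12h or more frequently as practical) until serum albumin is" at least 3.5 g/dL and no more than 0.5 g/dL below the pre-cycle value. The dosing instruction is "Interrupt ELZONRIS dosing until the relevant CLS sign/symptom has resolved". Table 4 in Section 7.5.5 and the serum albumin entry in Section 8.9 both send the reader to Appendix E.

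The Synopsis list of reasons to withhold an infusion has two more albumin rules:

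- At 3.0-3.5 g/dL, or on a fall of at least 0.5 g/dL from the start of the cycle, SL-401 is withheld and 25 g is given either daily or every 12 hours.
- Below 3.0 g/dL, or on a fall of more than 1.0 g/dL, SL-401 is withheld for the rest of the cycle and albumin is given until the level is above 3.5 g/dL. No amount or frequency is stated.

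**The concern.** The rules differ on when albumin is called for, and they interact badly. Section 7.3 treats 3.0-3.5 g/dL as a level at which dosing takes place, but Appendix E interrupts dosing below 3.5 g/dL. Once a patient at 3.2 g/dL is interrupted, the day becomes a withheld day, and Section 7.3's withheld-day threshold of 3.0 g/dL is not met. Applying one rule therefore removes the other's call for albumin.

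Capillary leak syndrome (CLS) is described in Section 3.8 as the principal dose-limiting toxicity, and intravenous albumin is among the mitigation measures named there. Sites could manage the same laboratory value differently and each cite the protocol. The difference could also reach the data. SAP Section 4.4.2.1 summarises albumin infusions and their timing relative to CLS onset, and the algorithm in SAP Section 8.3 counts any albumin value of 3 g/dL or less towards one of its criteria.

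**Working it through.** The plan states no figure to reproduce. The check sets the rules side by side and works out the daily amount each one calls for.

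Daily amounts:

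- Section 7.3 and Synopsis Allowed Medications/Therapies: 25 g x 1 = 25 g/day when triggered.
- Synopsis withholding rule (3.0-3.5 g/dL, or fall of at least 0.5): 25 g x 1 to 25 g x 2 = 25 to 50 g/day.
- Appendix E: 25 g x (24 h / 12 h) = at least 50 g/day.

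Applied to example values in g/dL, with fall = pre-cycle minus current:

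| Day | Pre-cycle to current | Fall | Section 7.3 calls for | Synopsis withholding bullets | Appendix E |
|---|---|---|---|---|---|
| Withheld | 3.6 to 3.2 | 0.4 | none | 25-50 g/day | at least 50 g/day* |
| Withheld | 3.7 to 3.2 | 0.5 | none | 25-50 g/day | at least 50 g/day |
| Withheld | 4.3 to 3.7 | 0.6 | none | 25-50 g/day | at least 50 g/day |
| Withheld | 3.6 to 2.9 | 0.7 | 25 g/day | albumin, amount not stated | at least 50 g/day |
| Dosing | 3.7 to 3.2 | 0.5 | 25 g/day | withhold; 25-50 g/day | interrupt; at least 50 g/day |
| Dosing | 4.3 to 3.7 | 0.6 | none | withhold; 25-50 g/day | interrupt; at least 50 g/day |

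*The Appendix E table is broken in the text available here, and the row for albumin below 3.5 g/dL shows no action of its own. This entry assumes it shares the action of the relative-fall row, which the 3.5 g/dL stopping level supports. The other Appendix E entries have a fall of at least 0.5 g/dL and do not need the assumption.

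The table separates two kinds of difference:

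1. Where Section 7.3 calls for 25 g/day and Appendix E for at least 50 g/day, only the frequency differs. An investigator who uses Section 7.3's discretion to give 25 g twice daily reaches 25 x 2 = 50 g/day, so this gap can close.
2. Where Section 7.3 calls for none, the triggers differ. This happens on withheld days at 3.0 to below 3.5 g/dL, and after a fall of at least 0.5 g/dL to a level outside Section 7.3's thresholds. Discretion over how often to give albumin does not settle the level at which to give it.

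Scope differs too. Appendix E has rows for before the first dose of cycle 1 and for the dosing period. Only Section 7.3 and the matching Synopsis paragraph address the immediate post-treatment period.

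**The case against.** The best defence is that the protocol already routes the reader to Appendix E. Table 4 and Section 8.9 both do so, and a patient held for albumin of 3.2 g/dL would normally be held under the very rule that also recommends replacement. Section 7.3 sits under allowed therapies, permits albumin whenever clinically indicated and leaves frequency open. The Synopsis withholding rule also calls for albumin in the withheld-day cases where Section 7.3 is silent.

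Much of this stands. It defeats the inference that a patient would receive either nothing or 50 g/day depending on the page consulted: where Section 7.3 gives no instruction, it gives no prohibition either. It also defeats the inference that infusions would be lost, since that requires a site to use Appendix E to hold the drug and then disregard it on replacement.

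The defence does not remove the conflict. Section 7.3 carries no cross-reference to Appendix E, no order of precedence is stated, and the albumin footnotes to Tables 5 to 8 refer only to the protocol in general. A permission is also weaker than a recommended action.

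**Conclusion.** The inconsistency is real and should be corrected. It concerns mainly the trigger. In the two situations identified above, Section 7.3 does not call for albumin, while Appendix E calls for at least 50 g/day. Elsewhere the difference is 25 against at least 50 g/day, which the investigator's discretion can close. At 3.0 to below 3.5 g/dL without a 0.5 g/dL fall, the result rests on reading the two Appendix E albumin rows as sharing one action. The conflict after a relative fall does not.

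Two stronger readings are not supported. Section 3.8 lists albumin alongside premedication, diuretics, monitoring and withholding without ranking them, so it cannot be called the main CLS mitigation. Nor do the documents show that CLS counts would change. In SAP Section 8.3 a low albumin value is one route to one criterion, and a case without the CLS preferred term needs two criteria starting within 7 days of each other. An effect on the albumin and CLS summaries is possible, but its size cannot be estimated from the documents.

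**What to change.** The sponsor's clinical team should reconcile four places: the Synopsis withholding bullets on albumin, the Synopsis Allowed Medications/Therapies paragraph, Section 7.3 and Appendix E. The result should be one rule stating trigger (absolute and relative), amount, frequency and target level. It should say explicitly what applies in the immediate post-treatment period, because replacing Section 7.3 with a pointer to Appendix E as it stands would drop that provision. The rule should appear once, with cross-references elsewhere. Which rule to adopt is a clinical decision on which this review takes no view. The cost is protocol wording in those four places, with no change to endpoints, sample size or analysis methods.

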7.4 Prohibited Medications/Therapies

Please refer to [Section 11](#) regarding investigational or approved anticancer agents prohibited during study participation.

7.5 SL-401

7.5.1 SL-401 Description and Storage

SL-401 is a novel biologic fusion protein comprised of recombinant human IL-3 genetically fused to truncated diphtheria toxin protein. SL-401 targets the IL-3R, which is over-expressed on the CSCs and/or tumor bulk of a variety of leukemias and hematopoietic malignancies, including BPDCN and AML, relative to normal hematopoietic stem cells and other hematopoietic cells.

SL-401 drug product is prepared in two formulations and dosage forms.

- SL-401 Injection is a non-preserved, sterile, liquid dosage form supplied in sterile 2 mL glass vials containing 1 mL of sterile SL-401 solution (1 mg/vial) and should be stored frozen at -20°C ($\pm 5^\circ\text{C}$).
- SL-401 for Injection is a non-preserved, sterile, powder for solution supplied in sterile 3 mL glass vials and should be stored at -20°C ($\pm 5^\circ\text{C}$).

Documentation stating the product's expiry date will be provided with each shipment.

7.5.2 Dose, Schedule and Duration of Treatment

SL-401 is administered by IV infusion over 15 minutes for 5 consecutive days of a 21-day cycle.

- In Stage 1, SL-401 is administered at escalating doses of at 7, 9, 12, or 16 $\mu\text{g}/\text{kg}/\text{day}$.
- In Stages 2-4, all patients will receive SL-401 at a dose of 12 $\mu\text{g}/\text{kg}/\text{day}$.

The dose of SL-401 will be dependent upon the patient's baseline body weight in kg (day of initial infusion for Cycle 1). This dose will be recalculated if there is a 10% (or greater) change in body weight from baseline. The aliquot is calculated from the $\mu\text{g}/\text{kg}$ dose \times patient weight in kg (including one decimal place; all patient doses are calculated in $\mu\text{g}/\text{kg}$ body weight). Dose changes should only occur once a cycle has been completed. Intra-cycle dose modifications will not be permitted.

Patients who benefit from treatment and do not have evidence of clinically significant progressive disease may receive repeated cycles of SL-401 even if a response, in the judgment of the Investigator, is not attained. Patients will continue to receive SL-401 as long as they may be benefiting from treatment, according to the Investigator; until the study is completed. No maximum duration of therapy has been set.

7.5.3 SL-401 Premedication and Dose Preparation and Administration

7.5.3.1 Premedication

Patients will receive the following premedication approximately 60 minutes before each SL-401 infusion:

- Acetaminophen 650 mg (or equivalent dose of paracetamol) orally (PO)
- Diphenhydramine 50 mg intravenously (IV) (or equivalent dose of another H1-histamine antagonist)
- Methylprednisolone 50 mg IV (or an equivalent dose of another corticosteroid)
- Ranitidine 50 mg IV (or an equivalent dosage of another H2-histamine antagonist)

7.5.3.2 SL-401 Dosage Preparation

SL-401 is prepared for administration by the pharmacy. The total per-patient dose is calculated based on patient body weight in kilograms (kg) including one decimal place, and the patient's assigned dose ($\mu\text{g}/\text{kg}$ dose \times patient weight in kg, including one decimal place [example: 7 $\mu\text{g}/\text{kg}$ \times 70.3kg]). The dose of SL-401 will be dependent upon the patient's baseline body weight in kg (day of initial infusion for Cycle 1). This dose will be recalculated if there is a 10% (or greater) change in body weight from baseline. Additional dose preparation supplies and instructions for both SL-401 formulations utilized in this study are described in detail within the Pharmacy Manual

7.5.3.3 Inpatient and Outpatient Setting for Dose Administration

The first cycle of SL-401 must be administered in the inpatient setting, with hospitalization beginning the day of the first infusion of SL-401 (or a prior day) and ending approximately 24 hours after the last infusion of SL-401. Subsequent cycles of SL-401 can be administered in

the inpatient setting or in a suitable outpatient ambulatory care setting that is equipped for intensive monitoring of patients with hematopoietic malignancies undergoing treatment, per the discretion of the Investigator and institutional guidelines and capabilities. Patients will be monitored for at least 4 hours following the administration of each infusion of SL-401.

7.5.4 Patient Monitoring Procedures During the SL-401 Dosing Period

To assess relevant acute toxicities, testing and procedures summarized below are to be performed and results are to be reviewed prior to each scheduled SL-401 infusion (refer to [Section 9.8](#) [Table 5](#), [Table 6](#), [Table 7](#), and [Table 8](#) for more detail):

- Vital signs including blood pressure, heart rate, respiration rate, body temperature, and pulse oximetry:
 - During daily dosing (usually Days 1, 2, 3, 4 and 5):
 - immediately prior to infusion,
 - immediately after completion of infusion, and
 - 30, 60, and 240 minutes post-infusion.
 - Days 8, 15, and 21.
- Diagnostic blood tests during daily dosing (usually Days 1, 2, 3, 4 and 5) and Days 8, 15, and 21 as follows:
 - Hematology: complete blood count (CBC) with differential, platelet count;
 - Serum Electrolytes and Chemistry: sodium, potassium, bicarbonate, chloride, blood urea nitrogen (BUN), creatinine, glucose, alanine aminotransferase (ALT), albumin, alkaline phosphatase (ALP), aspartate aminotransferase, (AST), bilirubin (total, direct, and indirect), calcium, creatine phosphokinase (CPK), magnesium, lactate dehydrogenase (LDH), phosphate, total protein, uric acid;
 - Coagulation: prothrombin time (PT) or International Normalized Ratio (INR), and activated partial thrombin time (aPTT).
- Routine urinalysis on Day 1 (prior to SL-401 infusion), and Days 8, 15, and 21.

7.5.5 Dose Delays/Modifications and Management Procedures for Toxicities Associated with SL-401

During the dosing period for each cycle, individual SL-401 infusions may be delayed to allow for toxicity resolution. Details are presented in [Table 4](#).

Monitor vital signs and check albumin, transaminases, and creatinine prior to preparing each dose of ELZONRIS.

Table 4: Recommended ELZONRIS Dose Modifications

Parameter	Severity Criteria	Dose Modification
Serum albumin	Serum albumin < 3.5 g/dL or reduced \geq 0.5 g/dL from value measured prior to initiation of the current cycle	See CLS Management Guidelines (Appendix E)
Body weight	Body weight increase \geq 1.5 kg over pretreatment weight on prior treatment day	See CLS Management Guidelines (Appendix E)
Aspartate aminotransferase (AST) or alanine aminotransferase (ALT)	ALT or AST increase $>$ 5 times the upper limit of normal	Withhold SL-401 until transaminase elevations are \leq 2.5 times the upper limit of normal.
Serum creatinine	Serum creatinine $>$ 1.8 mg/dL (159 micromol/L) or creatinine clearance $<$ 60 mL/minute	Withhold SL-401 until serum creatinine resolves to \leq 1.8 mg/dL (159 micromol/L) or creatinine clearance \geq 60 mL/minute.
Systolic blood pressure	Systolic blood pressure \geq 160 mmHg or \leq 80 mmHg	Withhold SL-401 until systolic blood pressure is $<$ 160 mmHg or $>$ 80 mmHg.
Heart rate	Heart rate \geq 130 bpm or \leq 40 bpm	Withhold SL-401 until heart rate is $<$ 130 bpm or $>$ 40 bpm.
Body temperature	Body temperature \geq 38°C	Withhold SL-401 until body temperature is $<$ 38°C.
Hypersensitivity reactions	Mild or moderate	Withhold SL-401 until resolution of any mild or moderate hypersensitivity reaction. Resume ELZONRIS at the same infusion rate.
	Severe or life-threatening	Discontinue SL-401 permanently.

Dose reductions should be discussed with the medical monitor on a case by case basis.

7.6 Treatment Discontinuation

7.6.1 Criteria for Treatment Discontinuation

SL-401 treatment may be discontinued for any of the following reasons:

- Patient withdrawal of consent
- Occurrence of unacceptable toxicity, including DLT
- SL-401 related anaphylaxis or Grade \geq 3 hypersensitivity reaction
- Requirement for $>$ 1 dose reduction unless there is evidence of AML/BPDCN response (beyond Cycle 1), in which case additional dose reductions are permitted, however these

reductions must be discussed with the Medical Monitor and documented in the context of ongoing AML/BPDCN response

- Disease recurrence/progression
- Intercurrent illness that prevents further administration of SL-401
- Patient non-compliance
- Occurrence of pregnancy
- Investigator's decision

The reason for SL-401 discontinuation and the date of discontinuation should be recorded in the eCRF.

In settings in which there is preliminary but not conclusive evidence of disease progression (i.e., new skin lesions of indeterminate etiology, new lymph nodes $\leq 1.5\text{cm}$, modest increase in bone marrow blast percentage subsequent to an initial marked reduction, appearance of new blast population on bone marrow evaluation by means of flow cytometry or other molecular methodology without increase in blast percentage consistent with PD), additional SL-401 cycles may be administered, provided that the Investigator documents that the evidence of potential disease progression is inconclusive and that the overall risk/benefit assessment favors additional investigational therapy. Additional SL-401 may also be administered in situations of mixed response BPDCN in which response/progression is not consistent between a given patient's disease sites, provided that the Investigator documents that the overall risk/benefit assessment favors additional investigational therapy. In such situations, it is essential that relevant findings and assessments are documented, and that areas of potential disease progression are followed closely on subsequent assessments.

7.6.2 Procedures and Follow-up after Treatment Discontinuation

The evaluation during which the Investigator determines that SL-401 will be discontinued should be considered the End of Treatment Evaluation; all tests and procedures for the End of Treatment Evaluation are listed in [Table 6](#) and [Table 8](#) (in [Section 9.8](#)). In addition, patients should be followed for a minimum of 30 days after the last infusion of SL-401 for assessment of AEs (including potential new AEs and potential change/resolution of existing AEs).

If the patient is in CR/PR at the time of discontinuation, disease assessments should continue to be performed as described in [Section 8.12](#) on an every 6-week basis (± 1 week) through 6 months post-C1D1 and then on an every 90-day basis or until, in the judgment of the Investigator, there is evidence of relapsed or progressive disease. Beyond the End of Treatment Evaluation and 30-day follow up (safety/AE assessment), it is requested that subsequent follow-up occur approximately every 90 days for survival status. (If the patient is in CR/PR at the time of discontinuation, disease assessments should continue to be performed as described in [Section 8.12](#) on an every 6-week basis (± 1 week) through 6 months post-C1D1 and then on an every 90-day basis or until, in the judgment of the Investigator, there is evidence of relapsed or

progressive disease. Patients who undergo SCT will be followed for the occurrence of VOD and engraftment delay or failure as part of survival monitoring.

If the patient discontinues SL-401 treatment and also withdraws consent for collection of future information, no further evaluations should be performed and no additional data should be collected as part of the study. The Sponsor will only retain and use any data collected before withdrawal of consent.

Please consult [Section 6.4](#) for recommendations concerning ongoing follow-up of patients alive with or without evidence of disease progression at the time of Study Completion/assessment of primary and critical secondary endpoints.

8 Study Procedures

